**Cardiac Disorders**

Bradycardia

**Eye Disorders**

Accommodation disorder  
Diplopia  
Extraocular muscles paresis  
Eyelid function disorder  
Eyelid ptosis  
Pupillary reflex impaired  
Vision blurred

**Gastrointestinal Disorders**

Constipation  
Dry mouth  
Dysphagia  
Ileus paralytic

**Infections and Infestations**

Botulism

**Musculoskeletal and Connective Tissue Disorders**

Muscular weakness

**Nervous System Disorders**

Bulbar palsy  
Cranial nerve palsies multiple  
Cranial nerve paralysis  
Dysarthria  
Facial paralysis  
Facial paresis  
Hyporeflexia  
Hypotonia  
Paralysis  
Paresis cranial nerve  
Peripheral nerve palsy  
Peripheral paralysis  
Speech disorder  
Vocal cord paralysis  
Vocal cord paresis

**Renal and Urinary Disorders**

Urinary retention

**Respiratory, Thoracic and Mediastinal Disorders**

Aspiration  
Diaphragmatic paralysis  
Dysphonia  
Dyspnoea  
Pneumonia aspiration  
Respiratory arrest  
Respiratory depression  
Respiratory failure

**Reproductive System and Breast Disorders**

Pelvic floor muscle weakness

## 6.3 Serious Adverse Events

The number and percent of patients with serious TEAEs will be tabulated by treatment groups (8 U/kg, 4 U/kg, and placebo) and overall for all serious adverse events regardless of relation to treatment by primary SOC and preferred term.

## 6.4 Clinical Laboratory Evaluations

Hematology and non-fasting clinical chemistry assays will be obtained at screening and exit as specified below.

Hematology	hemoglobin	hematocrit	red blood cells
	white blood cells	neutrophils	bands
	lymphocytes	monocytes	basophils
	eosinophils	platelets	
Electrolytes	sodium	potassium	bicarbonate
	chloride	phosphorus	calcium
Chemistry	glucose	creatinine	urea nitrogen
	total bilirubin	alkaline phosphatase (total plus bone and liver fractions)	aspartate aminotransferase (serum glutamic oxalacetic transaminase)
	alanine aminotransferase (serum glutamic pyruvic transaminase)	albumin	
Other	hemoglobin A1c	25 hydroxyl vitamin D	Parathyroid hormone if alkaline phosphatase bone fraction is abnormal

These values at each visit and the change from baseline will be summarized by the treatment group by visits using descriptive statistics. All laboratory values will be listed. Laboratory values at each visit will also be categorized as low, normal, and high according to the respective reference normal ranges.

## **6.5                    Vital Signs**

Vital signs are assessed at screening, day 1, and exit. Blood pressure (diastolic and systolic measured in mmHg), pulse rate (beats/minute), respiratory rate (breaths/minute), and body temperature (°C), weight (kg) will be summarized by treatment group for each visit and change from baseline to exit visit will also be summarized by treatment group.

## **6.6                    Columbia-Suicide Severity Rating Scale**

Suicidality for age over 6 years will be assessed using the Columbia-Suicide Severity Rating Scale (C-SSRS), conducted at every assessment visit. Suicide-related events corresponding to the C-SSRS questions will be classified into the following 11 categories:

- Self-injurious behavior, no suicidal intent
- Suicidal ideation
  1. Wish to be dead
  2. Active: Nonspecific (no method, intent, or plan)
  3. Active: Method, but no intent or plan
  4. Active: Method and intent but no plan
  5. Active: Method, intent and plan
- Suicidal behavior
  1. Preparatory acts or behaviors
  2. Aborted attempt
  3. Interrupted attempt
  4. Suicide attempt
  5. Completed suicide

The number and percentage of patients with the above suicide-related events during treatment will be presented by treatment group. If a patient has more than one suicide-related event during an interval, the most severe event in increasing order listed above will be used.

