12.1.18 Columbia-Suicide Severity Rating Scale (C-SSRS)

The C-SSRS (Posner et al, 2011) is a semistructured interview designed to assess the severity and intensity of suicidal ideation, suicidal behavior, and non-suicidal self-injurious behavior over a specified time period (eg, prior year, since last visit). The measurement of suicidal ideation is based on 5 “yes” or “no” questions (plus a description if answered “yes”) arranged in order of increasing severity. If the patient answers “yes” to either question 1 or 2, the intensity of ideation will then be assessed in 5 additional questions relating to the frequency, duration, controllability, deterrents, and reasons for the most severe ideation. Suicidal behavior is then assessed by asking further questions to categorize the behaviors into actual, aborted, and interrupted attempts; preparatory behavior; and non-suicidal self-injurious behavior. The interview is used in full only if the initial questions are positive; this assessment is completed at all scheduled clinic visits at which other clinical assessments are to be carried out.

If any item(s) on the C-SSRS are answered with “yes”, a physician investigator must review patient’s responses in order to:

- a) at screening and baseline determine patient's study eligibility and potential need for referral to a mental health professional, and
- b) during the study evaluate patient's need for appropriate medical management such as referral to a mental health professional.

A significant risk of suicide is defined as a “yes” in answer to: a) questions 4 or 5 on the suicidal ideation section; or b) any questions on any item in the suicidal behavior section. This must be reported as a serious adverse event and followed up accordingly (see Sections 9.1.2 and 9.3 of the study protocol). Additionally, if a patient responds “yes” to any of the suicidal ideation questions 1 to 3, the investigator should apply clinical judgment to determine the need for reporting as an adverse event or serious adverse event and the need for any referral.

The C-SSRS is available in several versions designed for use in clinical trials. Appropriate versions of the scale will be used in this trial.

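### The C-SSRS table in SAP 6.6 undercounts self-injury, and lower ideation levels, whenever a child has a higher-listed event in the same undefined interval

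*SAP*

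**What the plan says.** SAP 6.6 sets up the table: "Suicide-related events corresponding to the C-SSRS questions will be classified into the following 11 categories". The first entry, standing alone above the two headed groups, is "Self-injurious behavior, no suicidal intent". Five levels of suicidal ideation follow, starting with "Wish to be dead", and then five levels of suicidal behavior. The output is described as: "The number and percentage of patients with the above suicide-related events during treatment will be presented by treatment group". The next sentence gives the rule for multiple events: "If a patient has more than one suicide-related event during an interval, the most severe event in increasing order listed above will be used". The section does not say what an interval is.

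Protocol 12.1.18 describes the instrument and the reporting rule. When it explains how behavior is assessed, the list of what is categorized ends with "interrupted attempts; preparatory behavior; and non-suicidal self-injurious behavior". The opening sentence of the same section, however, names ideation, suicidal behavior and non-suicidal self-injury as three separate things. Significant risk, which must be reported as a serious adverse event, is a yes to "a) questions 4 or 5 on the suicidal ideation section; or b) any questions on any item in the suicidal behavior section". A yes to ideation questions 1 to 3 is left to the investigator's judgment.

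Protocol 7.3.4 and the opening of SAP 6 both promise the incidence of suicide-related events by treatment group.

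**The concern.** An incidence row should give the number of children who had that kind of event. Under the SAP rule, a row gives the number for whom that category was the highest reached in the interval. The two agree only if no child has two kinds of event in one interval.

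Non-suicidal self-injury is the most exposed row, because it is listed lowest and is treated as a step on the same ladder as ideation. A child who self-injures and also reports the mildest ideation is shown only under ideation. These events are expected to be few, so one or two children could be the whole content of a row and of any difference between arms.

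There is also a question of consistency with the protocol. If self-injury counts as an item of the suicidal behavior section, the table can show an event whose reporting is discretionary in place of one whose reporting as serious is mandatory.

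**Working it through.** **1. The SAP's own count.** 1 self-injury category + 5 ideation levels + 5 behavior levels = 11, as stated. Self-injury is rank 1 and wish to be dead is rank 2.

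**2. The rule applied to every pair of events in one interval.** There are 11 × 10 / 2 = 55 pairs, and the lower-listed event is dropped in each. A category of rank r is dropped in 11 − r pairs:
- self-injury (rank 1): 10 of the 10 pairs that include it;
- wish to be dead (rank 2): 9 of 10;
- ideation level 5 (rank 6): 5 of 10;
- completed suicide (rank 11): 0 of 10.

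Every row except the last can therefore be undercounted, and self-injury most often. Self-injury reported alone is still counted.

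**3. Overlap with mandatory serious reporting (protocol 12.1.18).** Count the pairs in which the dropped event must be reported as serious and the displayed one need not be.
- *Self-injury is an item of the behavior section.* The mandatory set is self-injury, ideation 4 and 5, and the five behavior levels. The discretionary set is ideation 1 to 3. The pairs are self-injury with ideation 1, 2 or 3, which makes 3. No other mandatory category can be hidden in this way, because all the others rank above ideation 3.
- *Self-injury is a separate domain.* It leaves the mandatory set, and the number of such pairs is 0.

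**4. The undefined interval.** Take a child with self-injury at week 4 and a wish to be dead at week 8. If the interval is the whole follow-up, only the wish to be dead is kept. If the interval is a visit, both survive. The C-SSRS is scheduled at five visits after treatment (weeks 2, 4, 6, 8 and 12), so the two readings can give different tables from the same data.

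**5. Comparison with adverse events.** In SAP 6.2 a patient is counted once for each preferred term. The worst-grade rule there acts on the severity of a given event, not across different kinds of event. SAP 6.6 collapses across kinds.

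**6. Size, under assumptions only.** The documents give neither the number of children aged 6 or more nor any event rate. The roughly 412 planned patients give 412 / 3 ≈ 137 per arm. Assume 50 to 90 of these are aged 6 or more.
- Effect of one hidden child on a row: 1/90 = 1.1 to 1/50 = 2.0 percentage points.
- Hidden children in the self-injury row = children × self-injury rate × share with a higher event in the same interval. Assume a rate of 2% to 5% and a share of 0% to 50%. The lowest value is 0, the midpoints give 70 × 0.035 × 0.25 = 0.6, and the highest is 90 × 0.05 × 0.5 = 2.25.

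As an assumed example, suppose 4 children in an arm self-injure and k of them also report a wish to be dead in the same interval. The planned row shows 4 − k, anything from 4 to 0. A separate row always shows 4.

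**The case against.** A worst-category table is a recognizable summary, and its second sentence can be read as the counting rule for the first rather than a contradiction of it. That is fair: the rule is coherent. It still does not yield the incidence of each category, which is what protocol 7.3.4 and SAP 6 promise.

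A reader might infer that self-injury which the protocol makes a serious adverse event vanishes from the safety report. The documents do not support this. Its mandatory status depends on one of two readings of protocol 12.1.18, and the SAP headings favor the other. On the reading that makes it mandatory, a treatment-emergent case is counted in the serious adverse event table of SAP 6.3. On either reading, SAP 2.3 has all data listed apart from commonly expected results. What remains is that a listing is not a by-arm count, and the SAP 6.3 table is by MedDRA term, not C-SSRS category. If self-injury is a separate domain, 12.1.18 gives no specific reporting rule for it, so the serious event table cannot be relied on to recover the count.

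A reader might also infer that the protocol ranks these events differently from the SAP. It does not rank them. It sets a reporting threshold, and seriousness and severity are defined separately in protocol 9.1.2 and 9.1.3. The issue to reconcile is how self-injury is classified.

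Finally, the size rests wholly on assumptions, and its range includes zero. That objection stands in full.

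**Conclusion.** The undercount follows directly from the stated rule. Within an interval, the self-injury row loses every child who also reports ideation or suicidal behavior, and lower ideation rows lose children in the same way. The claim that a mandatory serious event is hidden behind a discretionary one holds for three combinations on one reading of protocol 12.1.18 and for none on the other, so it should be put as an ambiguity to resolve.

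The consequence is limited to one descriptive table by treatment group. No test, power figure or efficacy conclusion depends on it. The figure of 0 to about 2 children per arm is an illustration; its upper end needs all three assumed inputs at their maximum. The change is still worth making, because the events are likely to be rare, the table is the planned by-arm summary of them, and correcting it costs little.

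**What to change.** In SAP 6.6:
- count each patient once in every category recorded after injection;
- show non-suicidal self-injury in its own row, outside the severity ranking;
- add rows for any suicidal ideation and any suicidal behavior;
- if a most-severe summary is wanted, keep it as an additional display;
- define the interval, for example as each visit or the whole period after injection.

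Separately, reconcile protocol 12.1.18 and SAP 6.6 on whether non-suicidal self-injury belongs to the suicidal behavior section, so that its classification and reporting status are stated once and used in both documents.

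The cost is some SAP wording and a few more rows in one table, with no new data. The category rows will no longer be mutually exclusive, so they will not sum to the number of children with any event, and a footnote should say so.

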## **6.7                   Immunogenicity Testing**

Blood samples (approximately 7 mL per visit) will be collected for immunogenicity testing at the screening visit and study exit from patients who weigh at least 15 kg at the screening visit. A 2-stage assay approach will be used for the detection of binding antibodies against BoNT-A and neutralizing antibodies against BOTOX in patients' serum. In stage 1, serum samples will be screened for reactivity using a validated enzyme-linked immunosorbent assay (ELISA). The reactive serum samples will be subsequently titered to assess the extent of antibodies present and immunodepleted to confirm that the reactivities are specific to BoNT-A. In stage 2, only samples that are confirmed positive in the ELISA will be tested for neutralizing antibodies to BOTOX using a validated assay.

Immunogenicity results of binding antibodies (BABs) against BoNT-A will be reported as positive or negative. Immunogenicity results of neutralizing antibodies (NABs) against BOTOX will be reported as positive, negative, or inconclusive. For NABs, the total negatives including patients with negative neutralizing antibody results as well as with negative binding antibody results will be reported.

Immunogenicity findings will be tabulated with the number and percent of patients at each visit separately for each treatment group. Percentages will be based on the number of treated patients with interpretable antibody assays in each treatment group at the specified visit. Antibody titers will be summarized by median, minimum, and maximum.

Depending on the timing and availability of data, immunogenicity data may be locked separately, at a different time point following the database lock for the main clinical data.

## **6.8                   Other Safety Analyses**

### **6.8.1               Physical Examination**

Physical examination will be performed at screening and study exit. Abnormal findings will be listed.

### **6.8.2               Pregnancy Test**

The urine pregnancy test will be performed for females of childbearing potential at screening, day 1 prior to injection and at study exit. Positive pregnancy test results (any pregnancies will be reported in the clinical study report) will be listed.

## 7                   **Interim Analyses**

No interim analysis is planned for this study.

## 8                   **Pharmacokinetic Data Analyses**

There will be no pharmacokinetic data to be analyzed from this study.

## 9                   **Health Outcomes Data Analyses**

There will be no health outcomes data to be analyzed from this study.

## 10                  **Analysis for US FDA HFD-550**

Analyses are as described in all preceding sections except for the items described below.

### 10.1               **Primary Efficacy Analyses**

There are 2 co-primary endpoints: the average grade change from baseline in the MAS-B ankle score with knee extended at weeks 4 and 6 and the average CGI by Physician at weeks 4 and 6. For both co-primary endpoints, the statistical null hypothesis is that both the higher dose (8 U/kg) and the lower dose (4 U/kg) have the same mean as placebo. The alternative hypothesis is that at least one study dose has a different mean than placebo. In addition to the primary statistical analyses cited in Section 5.2.1 for the average grade change from baseline in MAS-B ankle score with knee extended at weeks 4 and 6, the average CGI by Physician at weeks 4 and 6 will be analyzed using the same statistical method with a same MMRM model in Section 5.3.1.

The Hochberg procedure (Hochberg and Tamhane, 1987) will be used to control the family-wise type I error rate. With 2 doses and 2 co-primary endpoints in each dose, the maximum p-value for the 2 co-primary endpoints in each dose will be used in the Hochberg procedure. We first define the following values:

p11: p value for Botox 8 U/kg vs placebo comparing MAS-B

p12: p value for Botox 4 U/kg vs placebo comparing MAS-B

p21: p value for Botox 8 U/kg vs placebo comparing CGI

p22: p value for Botox 4 U/kg vs placebo comparing CGI

$p1 = \max(p11, p21)$ ,  $p2 = \max(p12, p22)$ .

$p_1$  and  $p_2$  will be sorted in an increasing order to get  $p(1) \leq p(2)$ . The following decision rule will then be applied:

Step 1: If  $p(2) \leq 0.05$ , both doses are considered efficacious; otherwise go to step 2.

Step 2: If  $p(1) \leq 0.025$ , its corresponding dose is considered efficacious; otherwise go to step 3.

Step 3: Neither dose is considered efficacious.

For sensitivity analysis purposes to supplement the co-primary analyses, ANCOVA using MI for missing values will be conducted for the co-primary endpoints of MAS-B ankle score with knee extended and CGI. The model will include baseline MAS-B ankle score with knee extended as a covariate and factors of age group, treatment group, study center, and previous botulinum toxin exposure. A summary of the percentages of missing MAS-B and CGI scores by visit will also be provided. Additional sensitivity analyses for the MAS-B ankle score with knee extended changes from baseline and CGI scores at each assessment timepoint will also be performed using the same ANCOVA with observed data, and linear contrasts will be used to estimate the treatment differences between each study dose and placebo.

## **10.2 Secondary Efficacy Analyses**

The secondary efficacy analyses will be the same as the statistical analyses cited in Section 5.3 except for the analyses for CGI by Physician which is described in the Section 10.1.

## **11 Data Collected but not Analyzed**

The date and signature of investigator and system required variables of electronic data capture (EDC) and IVRS/IWRS will not be analyzed.

## **12 Deviations from Protocol**

There are no deviations from protocol amendment 3.

## **14 Changes to Analyses**

*Changes to Analyses from Previous Version of Statistical Analysis Plan*

The changes to the analyses as specified in the last approved version of the statistical analysis plan, dated 01 NOV 2016, are as follows:

- Disposition summary will be performed for all randomized patients.
- Clarification on pooling for countries with less than 12 subjects enrolled. The country will be pooled to the smallest center in the same region (alphabetical order if there is a tie).

